3.3.2 Other significant adverse events (OAEs)

During the evaluation of the AE data, an AstraZeneca medically qualified expert will review the list of AEs that were not reported as SAEs and AEs leading to treatment discontinuation.

Based on the expert's judgment, significant AEs of particular clinical importance may, after consultation with the Global Patient Safety Physician, be considered OAEs and reported as such in the CSR. A similar review of laboratory, vital signs (pulse, blood pressure [BP] and weight), and/or ECG data will be performed for identification of OAEs.

Examples of these could be marked haematological and other laboratory abnormalities, and certain events that lead to intervention (other than those already classified as serious), dose reduction or significant additional treatment.

3.3.3 Laboratory data

Laboratory data will be collected throughout the study, from screening to follow-up visit as described in the CSP. Blood and urine samples for determination of haematology, clinical chemistry, and urinalysis will be collected as described in Section 5.2.1 of the CSP. For the definition of baseline and the derivation of post baseline visit values considering visit window and how to handle multiple records, derivation rules as described in Section 4 below will be used. Values recorded as "<x" will be reported as the maximum number of this range, i.e. x.

Change from baseline in haematology and clinical chemistry variables will be calculated for each post-dose visit on treatment.

Local reference ranges will be used for the primary interpretation of laboratory data at the local laboratory. Project reference ranges will be used throughout for reporting purposes.

3.3.4 Vital signs

Vital signs data obtained up until the 30 days from date of last dose of study treatment will be used for reporting. Change from baseline in vital signs variables will be calculated for each post-dose visit on treatment. For derivation of post baseline visit values considering visit window and to handle multiple records, derivation rules as described in Section 4 below will be used.

3.3.5 ECGs

Baseline is the pre-dose time point on the first dosing day (Day 1 Cycle 1). For each time point three ECG recordings should be taken within an approximate 5 minute period. The variables to be reported from the continuous ECG measurements are RR, PQ, QRS, and QT intervals. The QT interval will be corrected for RR (the duration of a heart beat) to obtain corrected (QTc) variables.

QTcF will be calculated using the formula:

$$QTcF = QT / RR^b$$

where $b = 1/3$.

To obtain a single value of QTcF, RR, PR, QRS and QT at each specified time point, the mean of the triplicate values at that time point will be used. For each subject, the change-from baseline in an ECG variable at each time point will be calculated as the difference between the mean of the replicate value at each post-dose time point and the mean of pre-dose baseline replicate value. All ECG data will be obtained from the vendor, eRT, and there will be no site interpretation.

QTc outliers are defined as QTcF values following dosing that are greater than 450 ms or are increases from baseline greater than 30 ms.

3.3.6 Left ventricular ejection fraction

Echocardiogram/MUGA data will be collected every 16 weeks throughout the study, from screening to treatment discontinuation as described in the CSP.

Change from baseline in LVEF will be calculated for each post-dose visit on treatment.

Abnormal LVEF are defined as values less than the lower limit of normal (project reference).

Absolute values will also be flagged if they meet either of the following criteria (considered as outliers):

- ≥ 10 percentage points decrease from baseline and $< 50\%$ LVEF, or

- ≥ 15 percentage points decrease from baseline and $\geq 50\%$ LVEF.

3.3.7 Duration of exposure and duration of treatment

Total and actual exposure will be calculated separately for AZD9291 or MEDI4736. Total exposure to each drug (AZD9291 or MEDI4736) will be time (days) from the first dose to the last dose:

$$\text{Total exposure} = (\text{last dose date where dose} > 0 \text{ mg} - \text{first dose date}) + 1$$

Actual exposure to each drug (AZD9291 or MEDI4736) will be time (days) from first dose to the last dose, taking account of dose interruptions.

$$\text{Actual exposure} = ((\text{last dose date where dose} > 0 \text{ mg} - \text{first dose date}) + 1) - \text{total duration of dose interruption (i.e., number of days with dose} = 0 \text{mg)}.$$

Dose reductions are not permitted per the CSP for MEDI4736. The actual exposure calculation makes no adjustment for any dose reductions that may have occurred.

The duration of treatment will be the time (days) from the first dose to the last dose of either treatment:

The last dose date for the combination arm is defined as the latest of the last non-zero dose of either agent. For the AZD9291 monotherapy arm, this will be the last non-zero dose of AZD9291.

$$\text{Duration of treatment} = (\text{last dose date where dose} > 0 \text{ mg} - \text{first dose date}) + 1$$

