1.2 Study design

This trial was initially designed as a phase III, multi-centre, open label, randomized study to assess the efficacy and safety of AZD9291 (80 mg, orally, once daily) in combination with MEDI4736 (10 mg/kg, IV infusion every 2 weeks [q2w]) versus AZD9291 monotherapy (80 mg, orally, once daily) in patients with a confirmed diagnosis of EGFR T790M mutation positive (T790M+) locally advanced or metastatic NSCLC (Stage IIIB-IV), who have progressed following prior therapy with an approved EGFR-TKI agent.

All patients must have documented radiological progression on EGFR-TKI treatment and on the last treatment administered prior to enrolling in the study.

A mandatory biopsy was needed for central testing of T790M mutation status following confirmed disease progression on previous treatment.

Three hundred fifty patients were planned to be randomized, however recruitment was stopped after enrolling 29 patients. Early termination of enrolment into the study was decided in the light of a higher than anticipated incidence of interstitial lung disease-like events in patients receiving the combination of AZD9291 with MEDI4736 in a separate multi-arm Phase 1b open label study D5160C00006 (TATTON).

Two summaries of the study data are planned:

Primary Summary

A primary summary will be performed with a data cut-off date representative of when the last country with active patients receives ethics and regulatory approval for protocol version 2.0. This summary will be used for the CSR and will report data according to the randomised or actual treatment groups as specified in [Section 2](#).

Final Summary

Patients had been initially randomized to receive either AZD9291 in combination with MEDI4736 or AZD9291 monotherapy. Depending on the treatment being received, the patients will be categorized as follows for the purpose of delineating the required study plan and assessments:

GROUP A - Patients on AZD9291 monotherapy

Group A includes patients continuing to receive AZD9291 monotherapy following data cut-off (DCO) for the primary analysis, who were either randomised to receive AZD9291 monotherapy or were randomised to receive AZD9291 in combination with MEDI4736 but who have discontinued MEDI4736 and been followed up for 90 days post discontinuation of MEDI4736

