Patients may continue dosing with the drug according to the protocol as long as they are continuing to show clinical benefit, as judged by the Investigator, and in the absence of a discontinuation criterion. These patients have no pre-scheduled visits until treatment discontinuation (apart those needed for the drug accountability and dispensing) and will follow the normal clinical site approach. Following approval of clinical study protocol (CSP) version 2.0 at the site only SAE, outcomes of pregnancy and drug dispensing/ accountability data will be collected for Group A patients. This may result in sparse data in some of the summaries in the primary summary.

GROUP B - Patients on MEDI4736 in combination with AZD9291 or MEDI4736 monotherapy

Group B includes patients randomised to receive MEDI4736 and AZD9291 and who are continuing to receive MEDI4736 either in combination with AZD9291 or as a monotherapy

Patients may continue treatment with MEDI4736 monotherapy or in combination with AZD9291 as long as they are continuing to show clinical benefit, as judged by the Investigator, and in the absence of a discontinuation criterion. Group B patients should follow the schedule / assessments specified in the CSP. Group B patients that discontinue MEDI4736 during the study can be switched to Group A and follow the AZD9291 Monotherapy assessment schedule following completion of the 90 day safety follow up. Following approval of CSP version 2.0

The overall study design is shown in Figure 1 below. The study schedule for Group A and Group B subjects is detailed in Tables 1 and 2 of the CSP, respectively.

[figure not shown]
A final addendum summary will be performed when the last patient discontinues MEDI4736 and completes their required safety follow up. All outputs from the primary summary will be repeated at the final summary, except those relating to change in tumour size at 6 weeks, which will have been fully reported during the primary analysis. Only data collected between

the primary summary data cut-off and the time when last patient receiving MEDI4736 reaches the end of safety follow up, will be summarised. If three or fewer patients are included in this summary, then only listings will be produced, with no summary tables.

If all patients have discontinued from MEDI4736 treatment at the time of DCO for the primary study summary, the primary summary will be the only summary of data for the study.

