1.3 Number of subjects

The original plan was to recruit approximately 350 subjects, stratified by current line of treatment (2nd/3rd line plus) and ethnicity (Asian/non-Asian), randomized in a 1:1 ratio to the treatments as specified below:

- AZD9291 80mg QD
- AZD9291 80mg QD and MEDI4736 10mg/kg q2w

The study was terminated early with only 29 patients randomized. This number is not considered sufficient for statistical comparison of the treatment groups, and all data reporting will be using summaries and listings.

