2.1.2 Safety Analysis Set

The Safety Analysis Set will consist of all subjects who received at least one dose of randomized treatment. Safety data will be summarized using the Safety Analysis Set, according to the treatment that patients received in their first cycle. Patients who received at least one dose of MEDI4736 in the first treatment cycle (15 +/-3 days) will be regarded as being in the combination treatment. Additional summaries might be provided for the patients who were randomised and received the combination but later discontinued MEDI4736 as appropriate.

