4.2.6 Exposure

Exposure will be listed and summarized for Safety Analysis Set. The following summaries will be produced:

- Summary of duration of exposure of AZD9291
- Summary of duration of exposure of MEDI4736
- Summary of duration of treatment for each arm
- RDI and PID of AZD9291
- RDI and PID of MEDI4736
- Summary of interruptions and reductions of AZD9291
- Summary of interruptions and delays of MEDI4736

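### Actual exposure to MEDI4736 is defined by a daily-dosing rule; applied as written to a 2-weekly infusion, it returns the number of infusions

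*SAP*

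**What the plan says.** SAP section 3.3.7 opens with "Total and actual exposure will be calculated separately for AZD9291 or MEDI4736". The calculation is done drug by drug, but with the same formula for each. Actual exposure "will be time (days) from first dose to the last dose, taking account of dose interruptions". The formula takes last non-zero dose date minus first dose date plus 1, and subtracts "total duration of dose interruption (i.e., number of days with dose" equal to 0 mg. The i.e. in that bracket makes the count of zero-dose days the definition of interruption, not an example of it.

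The two drugs have different schedules. Section 1.3 lists the combination arm as "AZD9291 80mg QD and MEDI4736 10mg/kg q2w", and section 1.2 describes the same 2-weekly infusion. The only sentence in 3.3.7 specific to MEDI4736 concerns dose reductions. Nothing there, or elsewhere in the SAP, exempts planned infusion-free days.

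Section 4.2.6 commits to a summary of the duration of MEDI4736 exposure and, as a separate item, to a "Summary of interruptions and delays of MEDI4736". Neither interruption nor delay is defined there for a 2-weekly infusion.

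**The concern.** For a drug taken every day, a day with dose 0 mg is a day off drug, and subtracting such days does what the section sets out to do. For a drug infused every 14 days, 13 days in each interval have no dose by design. Applied as written, the rule shows a fully compliant patient as interrupted almost throughout, and the difference between total and actual exposure no longer isolates delays or omissions.

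The primary objective is the safety and tolerability of the combination, and MEDI4736 exposure is part of the context in which those safety data are read. If the programmer follows the text, the actual-exposure figures mislead. If the programmer departs from it, the figures depend on an interpretation that the SAP has not fixed.

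**Working it through.** The SAP states no figure to reproduce, so the check applies its formula to dosing calendars.

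**Inputs.** MEDI4736 interval 14 days and AZD9291 daily (SAP 1.2 and 1.3); the total- and actual-exposure formulas (SAP 3.3.7). The SAP gives no distribution of infusions, so the calendars are worked cases. The dosing window *w* is not stated for MEDI4736 in general; 0 to 3 days is assumed.

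**As written.** Let there be *k* infusions, the first on day 1 and the last on day *L*.

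- Total exposure = *L*.
- Days with dose 0 = *L* − *k*.
- Actual exposure = *L* − (*L* − *k*) = *k*, whatever the spacing.

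On schedule, *L* = 14(*k* − 1) + 1 and zero-dose days = 13(*k* − 1).

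**Drug-specific rule.** Actual exposure = *L* − Σ(gap − 14), summed over gaps longer than 14 + *w* days.

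| Infusion days | Total | Actual as written | Total − actual as written | Actual, drug-specific | Total − actual, drug-specific |
|---|---|---|---|---|---|
| 2 on schedule | 15 | 2 (13.3%) | 13 | 15 | 0 |
| 3 on schedule | 29 | 3 (10.3%) | 26 | 29 | 0 |
| 6 on schedule | 71 | 6 (8.5%) | 65 | 71 | 0 |
| 12 on schedule | 155 | 12 (7.7%) | 143 | 155 | 0 |
| 6, one 14-day delay (1, 15, 29, 57, 71, 85) | 85 | 6 | 79 | 71 | 14 |
| 6, one 28-day delay (1, 15, 29, 71, 85, 99) | 99 | 6 | 93 | 71 | 28 |
| 5, one of 6 slots skipped (1, 15, 29, 57, 71) | 71 | 5 | 66 | 57 | 14 |

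The percentages are of total exposure. The last three rows are the same for *w* from 0 to 3.

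**In-window slip.** Infusions on days 1, 17 and 29 have gaps of 16 and 12 days. The drug-specific rule gives 27 of 29 days for *w* = 0 or 1, and 29 of 29 for *w* = 2 or 3.

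**Control: daily AZD9291.** Over 155 days without interruption the SAP formula gives 155; with 14 days off drug it gives 155 − 14 = 141. It works as intended there.

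**Alternative reading: only dosing records entered as 0 mg count.** If the skipped infusion above is logged as one 0 mg record, actual exposure is 71 − 1 = 70 (drug-specific rule: 57). If the 14-day delay has no 0 mg record, it is 85 − 0 = 85 (drug-specific rule: 71). The single patient with six infusions and one 14-day delay can therefore be reported as 6, 85 or 71 days.

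**What still shows the delay.** RDI (SAP 3.3.8) compares cumulative delivered with cumulative intended dose. If the last dose precedes progression, it is 6/7 = 85.7% for the 14-day delay, 6/8 = 75.0% for the 28-day delay and 5/6 = 83.3% for the skip, against 100% on schedule.

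**The case against.** The strongest reply is that nobody would call a planned infusion-free day an interruption, and that the SAP's own usage agrees. Section 2.2 treats interruption and delay as unplanned tolerability events. Section 4.2.6 pairs interruptions with delays for MEDI4736, which would be pointless if every patient with two infusions were interrupted. The formula's condition on non-zero doses suggests that records of 0 mg exist, so the bracket may refer to those records and not to empty calendar days. The 70- and 85-day figures also assume a particular eCRF layout that the SAP does not describe; interruptions might be held as start and stop dates.

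Most of this is fair as evidence of intent, and the last point stands: those two figures illustrate an assumed way of recording. But the SAP nowhere states the milder reading, and its bracketed definition says something else. A stated rule that gives a wrong result for one of its two named drugs is more than a missing detail.

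Two further objections concern the remedy. Any window threshold creates a jump: with a 3-day window a 17-day gap counts 0 days and an 18-day gap counts 4. And the interval in section 2.1.2, "at least one dose of MEDI4736 in the first treatment cycle (15 +/-3 days"), serves to assign patients to the combination group and is not stated to be a dosing window. Both are correct. The jump is a disclosed cost, and the window should come from the protocol.

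**Conclusion.** The formula is wrong as written for MEDI4736. Under the literal reading the result equals the number of infusions exactly, for any spacing; for 2 to 12 on-schedule infusions that is about 13% down to 8% of total exposure. These percentages are what the text produces if followed, not a prediction of what a programmer would deliver.

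The reach is small. The affected output is the descriptive MEDI4736 actual-exposure summary and listing in the combination arm of a study with 29 randomised patients and no hypothesis testing. The final summary is touched only if it is produced: if all patients have stopped MEDI4736 by the primary cut-off, "the primary summary will be the only summary of data for the study", and with three or fewer patients it consists of listings only. Total exposure, duration of treatment, RDI, PID and the AE tables do not use the term. The separate summary of MEDI4736 interruptions and delays still shows delays, provided that it does not borrow the 3.3.7 definition. RDI and PID are a partial safeguard, because under section 3.3.8 dosing after progression is left out of them.

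The correction should be made: the error is plain and the change is cheap. No efficacy or safety conclusion turns on it.

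**What to change.** Keep the present formula for AZD9291. In section 3.3.7 add for MEDI4736:

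1. Planned infusion-free days are not dose interruption. This sentence alone removes the error.
2. Interruption days are the sum over consecutive infusions of (gap − 14), counted only where the gap exceeds 14 days plus the dosing window allowed by the protocol. Delayed and skipped infusions both contribute; the section 4.2.6 summary may still report interruptions and delays as separate items.

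Total exposure, duration of treatment, RDI and PID need no change, and no dose or schedule is affected.

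The cost is two sentences and one derivation from infusion dates. The downsides are a drug-specific definition of interruption, the jump at the edge of the window, and steady drift inside the window going uncounted. For example, six infusions each 17 days apart with a 3-day window give total exposure 1 + 5 × 17 = 86 and interruption 0. Total exposure still reflects that drift, and so does RDI up to progression (6/7 = 85.7%).

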3.3.8 Dose intensity

Relative dose intensity (RDI) is the percentage of the actual dose intensity delivered relative to the intended dose intensity through to treatment discontinuation. Percentage intended dose (PID) is the percentage of the actual dose delivered relative to the intended dose through to progression. Both will be derived using the date of objective disease progression as defined by RECIST v1.1 using the investigator site assessments. If the investigator considered that it was in the patient's best interest to continue study treatment past this time, this was not included in the derivation of RDI and PID.

RDI and PID will be defined as follows:

- $\text{RDI} = 100\% * d/D$, where d is the actual cumulative dose delivered up to the earlier of progression (or a censoring event) or the actual last day of dosing and D is the intended cumulative dose up to the earlier of progression (or a censoring event) or the actual last day of dosing.
- $\text{PID} = 100\% * d/D$, where d is the actual cumulative dose delivered up to progression (or a censoring event) and D is the intended cumulative dose up to progression (or a

censoring event). D is the total dose that would be delivered, if there were no modifications to dose or schedule.

RDI and PID for AZD9291 and MEDI4736 will be calculated for the entire intended treatment period (censored at data cut-off).

3.4 PK and pharmacodynamics

3.4.1 Plasma concentrations of AZD9291 and metabolites AZ5104 and AZ7550

All plasma concentrations of AZD9291, AZ5104 and AZ7550 will be listed. Summaries of plasma concentrations by nominal sample window will be presented for the PK Analysis Set. Following approval of CSP version 2.0, PK samples were only collected in the combination treatment group.

The ratio of metabolite to AZD9291 in each PK sample will be listed. Summaries of ratio of metabolite to AZD9291 by nominal sample window will be presented for the PK Analysis Set.

The following summary statistics will be presented:

- The geometric mean (gmean, calculated as $\exp[\mu]$, where μ is the mean of the data on a logarithmic scale).
- Coefficient of variation (CV, calculated as $100 \sqrt{[\exp(s^2)-1]}$, where s is the standard deviation of the data on a log scale).
- Gmean \pm standard deviation (calculated as $\exp[\mu \pm s]$).
- Geometric Standard Deviation (GeoSD) calculated using transformed data.
- Arithmetic mean calculated using untransformed data.
- Standard Deviation calculated using untransformed data.
- Minimum, median, maximum and number of observations (n).

Non-quantifiable (NQ) values of plasma concentrations will be handled as follows:· If, at a given time point, 50% or less of the plasma concentrations are NQ, the gmean, CV, geoSD, arithmetic mean and standard deviation will be calculated by substituting the limit of quantification (LOQ) for values which are NQ.· If more than 50%, but not all, of the concentrations are NQ, the gmean, CV, geoSD, arithmetic mean and standard deviation will be reported as not calculable (NC). The max value will be reported from the individual data, and the min and median will be set as NQ.· If all the concentrations are NQ, the gmean and arithmetic mean will be reported as NQ and the CV, geoSD and standard deviation as NC.

The number of values above lower limit of quantification (LLOQ) will be reported for each time-point along with the total number of collected values. If data are available for less than

3 patients, no summary statistics other than minimum, maximum and n will be presented. The plasma concentration data for AZD9291 and its metabolites will also be analysed using a population PK approach, which may include exploring the influence of covariates on PK, if the data allows.

A pharmacokinetic-pharmacodynamic approach may be used to investigate the relationship between PK and selected primary, secondary and/or exploratory endpoints, where deemed appropriate. These results of these analyses will be reported separately from the study CSR. A separate data analysis plan will be prepared to describe such analyses.

3.4.2 Serum concentrations of MEDI4736

PK analysis of the serum concentration data for MEDI4736 will be performed by Clinical Pharmacology, AstraZeneca/MedImmune or delegate on behalf of Clinical Pharmacology.

The actual sampling times will be used in the PK calculations. Pharmacokinetic concentration data and summary statistics will be tabulated. Individual and mean blood MEDI4736 concentration-time profiles will be generated. PK parameters will not be reported as the data collected will not be sufficient for their determination.

